Abbreviations:

- IRB: Institutional Review Board
- ASES: American Shoulder and Elbow Surgeons Score
- SANE: Single Assessment Numeric Evaluation
- CRF: Case Report Form

RANDOMIZATION

The randomization plan will be produced using SAS v 9.2 for Windows. The sponsor will review preoperative paperwork; Informed Consent, Historical Record, and pre-operative American Shoulder and Elbow Surgeons Score prior to enrollment in the study and approve randomization for a subject based on those criteria that are evaluated and confirmed during or prior to the pre-operative visit. Control and accountability of the humeral investigational device will be managed in accordance with Sponsor SOPs.

Randomization must not occur until the surgical procedure has commenced, and the Intraoperative assessment of inclusion/exclusion criteria is completed. Patients who have met all eligibility criteria following the intraoperative assessment, and have signed the IRB-approved informed consent will be randomly assigned to one of two treatment groups. Patients will be randomized using a 1:1 blocked randomization scheme for investigational: control devices. Bilateral patients will be randomized by shoulder. See the Statistical Analysis Plan section for a specific description of the randomization scheme.

PATIENT MANAGEMENT

Table 1 summarizes the case report forms (CRFs) required during the course of the study. All surgery and follow up case report forms are recommended to be sent to Biomet Manufacturing Corp. within 2 weeks of the patient's operative/follow-up evaluation date. All Serious Adverse Events must be sent within 24 hours of the investigator's awareness of the event.

Pre- and post-operative clinical data will be collected by trained, authorized study personnel with the exception of patient-reported outcome assessments. Exhibit 11 contains an example of the Study Signature Log that will be utilized to document authorized study personnel. Clinical and patient reported outcomes will be collected on Case Report Forms (CRFs), as summarized in Table 1. Case Report Forms or checklists/worksheets may be used as source documentation when a complete source does not otherwise exist at the site.

Table 1: Screening and Follow-Up Clinical and Radiographic Exams						
Action	Pre- Operative	Intra- Operative	6-Weeks	3-Months	1-Year	2-Years annually thereafter***
Obtain written informed consent	x					
Complete subject screening and enrollment log	x					

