Demographic information will be collected so that valid comparisons can be made between the control and investigational groups. Detailed medical history will be obtained in accordance with the physician's clinic practice.

Eligibility will be determined by the collection of medical history, intraoperative criteria, and any other tests deemed relevant by the investigator and/or his or her institutional review board. Any tests that are to be conducted that are NOT part of the investigator's

normal clinical practice but are specific to this clinical study must be done after the patient has reviewed and signed the approved Informed Consent Form.

Clinical and Operative Assessments

An Operative Record Case Report Form will be completed to record details of group assignment, components implanted, and any operative complications. Post-operative clinical data will be collected utilizing recognized, validated scoring systems (ASES, Constant, and SANE scores). Radiographic images and Adverse Event data will be collected and submitted to the sponsor for independent assessment.

Radiographic Assessments

Three views are required for each study shoulder at each postoperative time point; glenohumeral Anterior-Posterior (AP) in internal and external rotation and axillary radiographs. All radiographic images will be assessed for radiolucencies, osteolysis, and component movement (subsidence, migration) by a centralized independent radiographic reviewer, utilizing the 6-week visit as the baseline radiograph.

PROTOCOL DEVIATION MANAGEMENT AND REPORTING

Any deviation from the FDA and IRB-approved study protocol or any other applicable regulatory requirements is considered a protocol deviation and must be reported to the sponsor using the Protocol Deviation Case Report Form (PD-100) as soon as they are known by the investigator.. Any Protocol Deviation will be assessed for effect on patient safety or the validity of the data. Please refer to the Statistical Analysis Plan section for details on how protocol deviations will be analyzed. According to 21 CFR Part 812.150(a)(4), an investigator shall notify the sponsor and the reviewing IRB of any deviation from the investigational plan to protect the life or physical well-being of a subject in an emergency. Such notice shall be given as soon as possible, but in no event later than 5 working days after the emergency occurred.

ADVERSE EVENT MANAGEMENT AND REPORTING

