Subjects who have been randomized to the Investigational or Control group in this study comprise the All Enrolled population. The co-primary endpoints will be analyzed for the All Enrolled population and the results will be compared to the primary analyses performed on the Analysis population to determine whether the results of this analysis are consistent for both populations. For patients in the All Enrolled Population who are missing data necessary for the determination of any of the co-primary endpoints at 22+ months, data will be imputed as described below in the section "Sensitivity Analyses."

ANALYSIS POPULATION

Subjects who have been randomized to the Investigational or Control group in this study and who have complete data for a primary endpoint collected per the protocol at 22+ months or who have had a revision or removal at or before 26 Months will be included in the Analysis Population. This is the population that will be used in the primary study analysis and determination of study success. Those subjects who are missing their primary endpoint at 22+ months will be included as part of the All Enrolled population described above. Subjects with protocol deviations will be analyzed on an individual basis to determine if they will be included in the Analysis Population.

MISSING DATA AND SENSITIVITY ANALYSES

Data will be considered "missing" for a given primary endpoint if this endpoint cannot be calculated or is not available for a subject in the All Enrolled population. If the subject has had a

device failure at any point on or prior to their 22+ month outcome, they will *not* be considered as missing data for the Absence of Revision/Removal/UADE endpoint, as this endpoint is cumulative. A subject who has had a revision or removal prior to two years will be considered a radiographic failure at the 22+ month time point for purposes of the primary analysis. When possible (i.e. the subject is seen by a study investigator in a non-emergency situation and collection of the data will not cause undue burden), ASES scores will be collected for these cases before the revision is performed in order to prevent these patients from missing knee scores in the primary efficacy analyses.

Sensitivity analyses will examine the sensitivity of the results to missing values of the primary outcomes using the following analyses:

Outcome Type	Analysis Description	
Binary	Tipping Point Analysis: Missing observations are replaced with	

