(Radiographic Success,	values until the lower limit of the 95% Confidence interval for the	
Absence of	difference in proportions is equal to the non-inferiority margin	
Revision/Removal))	(the tipping point). Graph will show which imputations of	
Kevision/Kemovaljj	success/failure for the missing values in the investigational and	
	control groups lead to a conclusion of inferiority, and which lead	
	to a conclusion of non-inferiority. Missing Values as Success: Imputation of missing values as	
	"success"	
	Missing Values as Failures: Imputation of missing values as	
	"failure"	
	lanure	
	Last Observation Carried Forward: Missing observations in	
	either group are imputed by taking the most recent outcome prior	
	to 24 months and using it in place of the missing 24-month	
	outcome.	
	2 Year In-Window Analysis : Only data collected within the 2-	
	year per-protocol visit window (22-26 months) are included in	
	this analysis.	
	Multiple Imputation: This method replaces each missing value	
	with a set of plausible values that represent the variability around	
	the choice of which value to impute.	
Continuous	Replace with Maximum: Imputation of missing ASES as "100"	
(ASES Score)		
	Replace with Minimum: Imputation of missing ASES as "0"	
	Last Observation Carried Forward: Missing observations in	
	either group are imputed by taking the most recent outcome prior	
	to 24 months and using it in place of the missing 24-month	
	outcome.	
	2 Year In-Window Analysis : Only data collected within the 2-	
	year per-protocol visit window (22-26 months) are included in	

this analysis.
Multiple Imputation: This method replaces each missing value
with a set of plausible values that represent the variability around
the choice of which value to impute.

In addition, in the event that one or more subjects receive the opposite treatment than the one they were randomized to receive, a sensitivity analysis will be done on patients "as randomized" to make sure it is consistent with the primary analysis ("as treated"). However, because randomization will be performed intra-operatively and the patient must be able to receive either treatment in order to be randomized, this situation is not expected to occur. Other sensitivity analyses will be conducted as needed (i.e. if the effect of missing data on a particular primary outcome is still unclear).

TESTS FOR INTERACTION

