As with any surgical procedure, there are risks involved with total joint replacement surgery. Potential adverse events include, but are not limited to:

- 1. Complications resulting from anesthetic
- 2. Damage to nerves and blood vessels
- 3. Allergic reactions to the implanted devices
- 4. Phlebitis
- 5. Long-term swelling
- 6. Pulmonary embolus
- 7. Delayed wound healing
- 8. Prolonged illness
- 9. Hematoma
- 10. Wound dehiscence and/or drainage
- 11. Excessive bleeding that may result in the need for blood transfusions and/or further surgery
- 12. Permanent pain, deformity; and inconvenience.
- 13. Permanent brain damage
- 14. Pneumonia
- 15. Venous thrombosis
- 16. Heart attack
- 17. Kidney failure

GENERAL RISKS ASSOCIATED WITH TOTAL SHOULDER REPLACEMENT

- 1. Early or late infection perhaps necessitating device removal
- 2. Component dislocation and subluxation
- 3. Fracture or perforation of the bone (intraoperative or post operative)
- 4. Fracture, perforation, delamination (failure of the porous coating materials to adhere to the implant) of the device (intraoperative or post operative)
- 5. Device loosening or migration
- 6. Fretting or corrosion of implant interfaces
- 7. Wear and/or deformation of articulating surfaces
- 8. Particulate wear debris may initiate a cellular response leading to osteolysis
- 9. Damage to surrounding tissues, cartilage, or tendons
- 10. Inadequate range of motion
- 11. Persistent pain
- 12. Implantation of the device may require greater surgical exposure and prolonged surgical time
- 13. Instability
- 14. Periarticular calcification or ossification, with or without impediment of joint mobility
- 15. Undesirable shortening of limb
- 16. Disassociation of humeral head from humeral stem/component
- 17. Reoperations of the index shoulder to address post operative soft tissue pathologies (eg. Exploration of the brachial plexus, soft tissue release, long head of bicep pathology, rotator cuff tearing including subscapularis rupture/insufficiency, or soft tissue instability)

Rarely some adverse events may be fatal. These possible adverse events are not unique to the Comprehensive[®] Shoulder System with nano humeral component and, as stated above, may occur with any total joint replacement surgery.

Limitation may be imposed depending upon the patient's age, general health, baseline (preoperative) activity level and baseline (pre-operative) condition of the shoulder and other joints.

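### Co-primary (b) has two conflicting definitions, and the 'as treated' label on the deciding analysis leaves it open which arm bears an intra-operative failure that ends in a crossover

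*Combined protocol and SAP*

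**What the plan says.** **Definition of (b).** The Co-Primary Endpoints section gives a composite: no unanticipated device-related event; no fracture or perforation of bone and no dislocation; no fracture, perforation or dissociation of the device; no revision or removal. The sample-size text for this endpoint builds its 95% success rate from 2% revision, 2% bone fracture or perforation and 1% dislocation. The SAP hypothesis for this endpoint, the definitions of p_I and p_C in its sample-size section, and the Study Summary name only revision, removal or UADE. The sensitivity-analysis table drops UADE as well. The Study Definitions exclude from UADE any event listed in Section C, and Section C lists "Fracture or perforation of the bone (intraoperative or post operative").

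**Grouping.** Of the Analysis Population the SAP says "This is the population that will be used in the primary study analysis and determination of study success". It defines that population by randomisation, but adds "Subjects with protocol deviations will be analyzed on an individual basis to determine if they will be included in the Analysis Population", without criteria. The closing paragraph of Missing Data and Sensitivity Analyses provides an as-randomised analysis, if anyone receives the opposite device, "to make sure it is consistent with the primary analysis ('as treated". That parenthesis is the only place where the deciding analysis is called as treated. The paragraph adds that, because the patient must be able to receive either device, "this situation is not expected to occur". On timing, the Randomization section says "Randomization must not occur until the surgical procedure has commenced, and the Intraoperative assessment of inclusion/exclusion criteria is completed". The co-primaries are also analysed in All Enrolled "to determine whether the results of this analysis are consistent for both populations". No consequence is stated if either check disagrees with the primary analysis.

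**The concern.** A co-primary endpoint must give one verdict per shoulder, and here an unrevised fracture gets two. Whoever programs the analysis must choose between them, possibly after seeing how many fractures fell in each arm.

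The grouping question matters because eligibility for both devices is confirmed before the assigned one is seated. That check cannot exclude a fracture during seating. If such a shoulder were converted from nano to mini stem, an as-treated analysis would ordinarily count it in Control. It would also fall under the protocol's broad rule, "Any deviation from the FDA and IRB-approved study protocol or any other applicable regulatory requirements is considered a protocol deviation", so the case-by-case review could remove it. In both cases a failure that arose under the nano assignment would leave the nano arm, on a safety endpoint with a 10-point margin.

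**Working it through.** **1. Reproduce the plan's figure for (b).** Inputs from the SAP: p = 0.95 in both arms, margin 0.10, one-sided alpha 0.05, power 90%.

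n = (1.645 + 1.282)² × 2p(1−p) / 0.10²

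- p = 0.95: n = 81.4, so 82 per arm; 82/0.85 = 96.5, so 97. Both match the plan.
- p = 0.98 (the 2% revision rate alone, with UADE taken as zero): n = 33.6, so 34 per arm.

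The plan's 82 therefore belongs to the composite. Of the 5 points of expected failure, 2 + 1 = 3 come from bone fracture or perforation and dislocation, which the SAP hypothesis does not name.

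**2. One shoulder under the two definitions.** Take a bone fracture with no revision.

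| Text | Rule | Result |
|---|---|---|
| Co-Primary Endpoints | bone fracture is a failure | failure |
| SAP hypothesis | revision, removal or UADE only; a Section C risk is not a UADE | success |

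Dislocation, dissociation and device fracture or perforation are also listed in Section C, so the same split applies to them when no component is revised.

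**3. Effect of one converted failure, using the composite.** The bound is the SAP's one-sided Wald limit, taken as nano minus Control: (p_I − p_C) − 1.645 × √[p_I(1−p_I)/n_I + p_C(1−p_C)/n_C]. Non-inferiority needs at least −10 points. The failure counts are assumptions.

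Worked case, 112 per arm, 11 nano and 6 Control failures:

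- As randomised, 11/112 vs 6/112: −4.46 − 1.645 × 3.53 = −10.3, fails.
- One moved to Control, 10/111 vs 7/113: −2.81 − 1.645 × 3.54 = −8.6, passes.
- One excluded, 10/111 vs 6/112: −3.65 − 1.645 × 3.45 = −9.3, passes.

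| Per arm | Failures, nano vs Control | As randomised | Moved | Excluded |
|---|---|---|---|---|
| 112 | 10 vs 6 | −9.2 | −7.6 | −8.3 |
| 112 | 11 vs 6 | −10.3 | −8.6 | −9.3 |
| 112 | 12 vs 6 | −11.3 | −9.7 | −10.4 |
| 132 | 14 vs 7 | −10.8 | −9.4 | −9.98 |
| 132 | 7 vs 7 | −4.5 | −3.1 | −3.7 |

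**4. False-positive rate of test (b) alone.** Simulation with 2,000,000 trials per cell, 112 and 132 per arm, true failure 15% nano and 5% Control, so nano sits exactly at the margin. Converted failures are part of the 15% (and of the 5% where they occur in Control). The conversion rates are assumptions.

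| Converted failures | As randomised | As treated | Excluded |
|---|---|---|---|
| none | 6% | 6% | 6% |
| 0.5 points, nano only | 6% | 9% | 7% |
| 1 point, nano only | 6% | 13% | 9% |
| 1 point in each arm | 6% | 6% | 6% |

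The 6% under as-randomised grouping is the Wald interval's own behaviour at these sizes and is not caused by crossover.

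**The case against.** The strongest reply concerns the second part. No section describes a fracture followed by conversion, and the plan gives a reason for expecting no crossover: allocation is revealed in theatre, after suitability for either device is confirmed. With no crossovers the two groupings coincide. An as-randomised analysis is triggered by any crossover, and All Enrolled gives another check. The cases that change the verdict need roughly twice as many nano as Control failures; at 10 vs 6 the as-randomised test already passes. All of this stands, and it makes the second part conditional.

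A reader might infer that the plan necessarily removes a converted nano failure from the nano arm. The documents do not support that. The label stands only in a parenthesis, the Analysis Population is defined by randomisation, and individual review may retain the shoulder. A nano component seated and then exchanged might also count as a revision under the Study Definitions and stay a nano failure. The text leaves the handling unsettled.

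A reader might also take the 2% bone fracture or perforation rate as a conversion rate, which would put the as-treated false-positive rate at 24–26%. That would require every such event to be intra-operative, converted and confined to nano. The SAP gives no such split.

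Which grouping should lead in a non-inferiority trial is a fair debate, since as-randomised analysis can dilute a real difference. None of these replies touches the conflict over (b), which needs no crossover and no assumed rate.

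**Conclusion.** Part one is certain from the text: endpoint (b) has two definitions that disagree on an unrevised fracture, and only the composite matches the 95% assumption and the 82 per arm.

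Part two holds conditionally. The deciding analysis carries an as-treated label that the population definition does not share, deviators are judged without criteria, and a discordant check has no stated consequence. If failed conversions run mainly from nano to mini stem and are moved or dropped, one shoulder can change the verdict near the margin, and the false-positive rate of (b) alone rises from about 6% to about 9% or 13% as treated with 0.5 or 1 point of nano-only converted failures. Away from the margin one shoulder changes nothing, and with no or balanced failed conversions there is no inflation. Success needs all three endpoints, so the trial-level rate cannot exceed these figures. They assume the composite; under the SAP hypothesis an unrevised fracture might not be a failure in either arm. Both parts should be fixed.

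**What to change.** 1. Restate the SAP hypothesis for (b) and the matching sample-size definitions, with the Study Summary and sensitivity-table labels, so that the endpoint tested is the composite in Co-Primary Endpoints.
2. For the primary analysis, keep every implanted shoulder in its randomised arm and count its intra-operative events for (b). Do not remove crossovers or other deviators from this set by individual review.
3. Report as-treated and per-protocol results as supportive, with a fixed exclusion list applied blind to arm before database lock. State what follows if they disagree with the primary result.
4. As a minor alignment, reconcile enrolment defined as receipt of a device (Discontinuations and Revisions) with All Enrolled defined by randomisation. Shoulders randomised but not implanted may still be replaced, but should be reported by arm.

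The cost is low. Both groupings are already planned and exchange roles, with no added patients, visits or data. The change needs IRB approval and, if necessary, FDA approval. The drawback is possible dilution under as-randomised analysis, which the supportive analysis in item 3 is there to expose.

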Complete eligibility checklist	x					
Complete Patient History Form: HX100	x					
Complete ASES Assessments: ASES100	x		х	x	х	х
Complete SANE Assessment: SANE100			x	x	x	х
Complete Constant Score Form: CST100	х		X**	x	х	х
Randomize Patient		х				
Record Operative Details: OP100		х				
Collect Radiographic Images (AP Int., AP Ext, and Axillary Views)			x	x	x	x
Protocol Deviation Form: PD100	As needed	As needed	As needed	As needed	As needed	As needed
Complete Adverse Event Form: AE100 and/or Serious Adverse Event SAE100	As needed	As needed	As needed	As needed	As needed	As needed
Complete patient Withdrawal Form: WD 100		As needed	As needed	As needed	As needed	As needed
Complete Device Revision/Removal: RR100			As needed	As needed	As needed	As needed

Each follow-up visit time point will be determined based on the date of surgery.

** At the 6 week interval, in order to protect the subscapularis repair, the strength and ROM sections are not to be completed by sites.

*** Annual follow up will continue until study closure or until the last enrolled patient reaches their 2 year follow up window.

BILATERAL PATIENTS

A patient undergoing staged bilateral surgery must sign a consent form **for each study procedure**. Each study shoulder will be randomized separately. Bilateral patients will be required to wait at least 9 months between procedures for the purposes of the study.

Patients with staged bilateral study implants will require two ASES, Constant Score, and SANE assessment forms to allow individual assessment of each operative side over the course of the study. Patients must be instructed to assess each shoulder individually, i.e., only record right-shoulder pain levels on the CRF for their right shoulder and only report left shoulder pain on the CRF for the left shoulder.

SCHEDULE OF FOLLOW-UP ASSESSMENTS

Post-operative clinical and radiographic evaluations will be performed according to the following schedule, with the associated visit windows:

- 6 weeks (± 2 weeks)
- 3 months (± 2 weeks)
- 1 year (± 2 months)
- 2 years (± 2 months)
- Annually thereafter* (± 2 months)
- * Until all patients reach the 2-year visit window or the study is closed

ASSESSMENT PARAMETERS AND METHODS

Pre-Operative Visit - Medical History, Demographic Data and Patient Eligibility

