Balanced, blocked randomization (1:1, Investigational: Control) will be implemented. Randomization will be per shoulder, and each shoulder will count as a separate case toward the total sample size. In the event that a screen failure occurs post-randomization, randomization will not be reassigned and this shoulder will not count toward the overall sample size. Randomization will continue with the next shoulder enrolled as previously described until the minimum sample size is reached in both treatment groups. Randomization will be blocked by site, and each site will receive separate randomization plans using a predetermined block size that will remain undisclosed to the sites.

SAMPLE SIZE CALCULATION INITIAL SAMPLE SIZE CALCULATIONS AND ASSUMPTIONS

The primary objective of this study is to show that the Investigational device is non-inferior to the Control device with respect to three co-primary endpoints at 22+ months. The sample size for each endpoint was calculated, and the largest chosen as the sample size for this study. The endpoint requiring the largest sample size was Radiographic Success; therefore the sample size for this study will be the one described immediately below. For reference, the sample size for the other two endpoints is shown as well.

Radiographic Success

Non-inferiority sample size calculations were implemented in nQuery Advisor 7.0 software using a 1:1 ratio of Investigational to Control subjects. This software uses methodology as described in a text by Farrington and Manning⁵.

The sample size needed to obtain 90% power for testing for non-inferiority of the investigational device to the control device with regard to radiographic success was calculated as follows:

⁵ Farrington and Manning. "Test statistics and sample size formulae for comparative binomial trials with null hypotheses of non-zero risk difference for non-unity relative risk". *Statistics in Medicine* 9(1990) pp 1447-1454.

Definitions:

 p_I : Proportion of Radiographic success in the Investigational treatment group

 p_C : Proportion of Radiographic success in the Control treatment group.

δ: Non-inferiority margin. Lower 95% confidence bound for difference in proportions of clinically successful subjects at 22+ months (Investigational – Control) must be greater than -δ.

For a specified constant, $0 < \delta < 1$, the hypotheses of non-inferiority are:

 $H_0: \ p_I - p_C \le -\delta \ vs. \quad H_A: \ p_I - p_C > -\delta.$

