The association between the primary endpoints and device group at 22+ months across investigators will be examined using either an analysis of variance model (for ASES score) or the Breslow-Day test for homogeneity of odds ratios (for Radiographic Success and Absence of Revision/Removal/UADE). These tests for interaction will use a p-value of 0.10. If there is no evidence of treatment *center interaction ($p \ge 0.10$) for a particular outcome, data will be pooled across centers for that outcome. If p < 0.10, then this outcome for each site will be examined graphically to assess site dependency as well as whether or not a qualitative interaction exists. Further, the sites contributing to this interaction will be examined, and if necessary, a stratified analysis will be conducted and results compared to overall study results to assess consistency.

In addition, the association between device group and the primary endpoints for unilateral and bilateral subjects will be examined using either an analysis of variance model (ASES) or the Breslow-Day test for homogeneity of odds ratios (Radiographic Success and Absence of Revision/Removal/UADE). As before, a significant p-value (p <0.10) for a particular outcome indicates heterogeneity in that outcome for unilateral and bilateral subjects; if this occurs, that outcome for each group will be examined graphically and descriptively to assess these differences. Primary outcomes for unilateral and bilateral subjects will also be compared using a Fisher's exact test (Radiographic Success and Absence of Revision/Removal/UADE) or a pooled t-test (ASES). If p<0.10 for the two-way comparison or the test for interaction, the

bilateral subjects will be compared as a separate group for that outcome, and additional unilateral subjects may be enrolled (via IDE supplement/protocol amendment) in order to protect statistical power of the primary study analysis.

PROTOCOL DEVIATIONS

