BASELINE CHARACTERISTICS

Subjects in the Investigational and Control study groups will be compared regarding a list of baseline items, including preoperative ASES and Constant Scores, demographics (age, gender, and primary diagnosis), medical history, and comorbidities.

EFFICACY EVALUATIONS

Primary Endpoint

The confidence intervals used in the analysis of the binary primary endpoints (Radiographic Success and Absence of Revision/Removal/UADE) will be 1-sided, 95% confidence intervals for the difference between proportions in two independent samples. They will be calculated using the Wald method as based on a normal approximation to the binomial, as follows:

$$(p_C - p_I) + z_\alpha \sqrt{SE_C^2 + SE_I^2}$$

Where

 p_{C} = proportion of success in the Control group, p_{I} = proportion of success in the Investigational group, α = 0.05, and

$$SE_C = \sqrt{\frac{p_C(1-p_C)}{n_C}}$$
 and $SE_I = \sqrt{\frac{p_I(1-p_I)}{n_I}}$

The confidence interval used in the analysis of the continuous primary endpoint (ASES Score) will be a 95% confidence interval for the difference between means in two independent samples. They will be calculated using the normal distribution, as follows:

$$(\overline{x}_C - \overline{x}_I) + z_\alpha \sqrt{\frac{s_C^2}{n_C} + \frac{s_I^2}{n_I}}$$

Where

 x_{C} = mean ASES score in the Control group,

 $\overline{x_{I}}$ = mean ASES score in the Investigational group,

 $s_{\scriptscriptstyle C}$ = standard deviation of the ASES scores for the Control group,

 s_{T} = standard deviation of the ASES scores for the Investigational group, and

 $\alpha = 0.05$

Secondary Endpoints

Secondary outcomes include the ASES score, SANE score, Constant score, and radiographic endpoints at 6 weeks, 6 months, 1 year, and 2 years separately. These outcomes will be compared for Investigational and Control groups at each time point.

Exploratory Analyses14

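### The ASES comparison of unilateral with bilateral subjects ignores correlation between a patient's two shoulders, so its 10% trigger fires falsely more often than stated (about 13-21% under assumed correlations of 0.3-0.7)

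*Combined protocol and SAP*

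**What the plan says.** Under Randomization Details the SAP makes the shoulder the unit: "Randomization will be per shoulder, and each shoulder will count as a separate case toward the total sample size". The protocol section Bilateral Patients agrees ("Each study shoulder will be randomized separately") and asks a staged bilateral patient for two ASES forms, one per side. One patient can therefore supply two ASES outcomes.

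Under Tests for Interaction, unilateral and bilateral subjects are compared on each co-primary endpoint in two ways. The first is a treatment-by-laterality interaction test. The second is a direct comparison: "Primary outcomes for unilateral and bilateral subjects will also be compared using a Fisher's exact test" for the binary endpoints, and for ASES a "pooled t-test (ASES). If p<0.10 for the two-way comparison or the test for interaction, the" consequence follows: "bilateral subjects will be compared as a separate group for that outcome, and additional unilateral subjects may be enrolled", by IDE supplement or protocol amendment, to protect the power of the primary analysis.

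The documents name no paired, clustered or mixed-model method and no within-patient correlation. They give no expected share of bilateral patients and do not define bilateral for this test.

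**The concern.** A pooled t-test assumes independent observations. In the device comparison, a patient's two shoulders may land in the same arm or in opposite arms, and the covariance terms cancel on average. In the unilateral-versus-bilateral comparison they cannot cancel, because both shoulders are in the bilateral group by definition. If the two scores are positively correlated, the variance of the bilateral mean is understated and the test rejects too often.

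The test has consequences. A false trigger splits the analysis of a co-primary endpoint and can prompt a protocol amendment with more enrolment. The 10% level is the plan's statement of how often that happens by chance, and the named test does not deliver it for ASES.

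**Working it through.** **Inputs from the documents.** ASES SD 19, margin 9.5, one-sided alpha 0.05, 90% power, 70 per arm. Radiographic success 93% in both arms, margin 0.10, 112 per arm. 15% attrition, 132 per arm. Trigger p<0.10, taken as two-sided.

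**Assumed, because the documents are silent.** Within-patient correlation r; number of patients m with both shoulders in the study; shoulder-level testing, inferred from Randomization Details.

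**The plan's own figures.**
- ASES: n = 2 × 19² × (1.645 + 1.282)² / 9.5² = 68.5, so 69, or 70 with the noncentral t. 70/0.85 = 82.4, so 83.
- Radiographic: n = 2 × 0.93 × 0.07 × (1.645 + 1.282)² / 0.10² = 111.5, so 112. 112/0.85 = 131.8, so 132.

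All match. Evaluable shoulders: N = 2 × 112 = 224. The plan gives no false-trigger rate beyond the nominal 10%.

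**Variance of the comparison.** Let f = 2m/N be the share of shoulders in pairs. The true variance of the bilateral mean is SD² × (1 + r)/(2m), while the pooled t-test uses SD²/(2m). For the difference in means:

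true variance / assumed variance = [(1 + r)/(2m) + 1/(N − 2m)] / [1/(2m) + 1/(N − 2m)] = 1 + r(1 − f)

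actual size = 2 × [1 − Φ(1.645 / √(1 + r(1 − f)))]

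The SD cancels. Example with m = 20, r = 0.5: f = 40/224 = 0.179; ratio = 1 + 0.5 × 0.821 = 1.411; 1.645/√1.411 = 1.385; size = 16.6%.

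| Pairs (N = 224) | r = 0.3 | r = 0.5 | r = 0.7 |
|---|---|---|---|
| 5 | 14.7% | 17.6% | 20.3% |
| 10 | 14.5% | 17.3% | 19.9% |
| 20 | 14.1% | 16.6% | 19.0% |
| 40 | 13.2% | 15.3% | 17.2% |

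Simulation at N = 224 (20,000 trials per setting) agrees: 13.0% to 20.6% over 5-40 pairs and these correlations, and about 10% when r = 0. For r from 0.1 to 0.9 and f from 5% to 50%, the formula gives about 11% to 23%.

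**If bilateral includes patients with one study shoulder.** With f = 10% as the bilateral group and half of it unpaired, the ratio is 1 + 0.5 × r × 0.9. The size is 12.3% at r = 0.3 and 15.1% at r = 0.7.

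**Cost of a false ASES trigger.** Setting aside 20 pairs, split evenly, takes 112 per arm to 92.
- 112 per arm: SE = 19√(2/112) = 2.539; power = Φ(9.5/2.539 − 1.645) = Φ(2.10) = 98.2% (98.1% with the noncentral t).
- 92 per arm: SE = 2.801; power = Φ(3.391 − 1.645) = Φ(1.75) = 96.0% (95.9% with the noncentral t).

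At 20 pairs the trigger fires in an extra 4-9% of trials, each losing about 2.2 points. The average loss is 0.1-0.2 points. Even 40 pairs set aside would leave 72 per arm, above the 70 that ASES needs.

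**Check of the remedy.** With one mean per bilateral patient and an unequal-variance t-test, the simulated size is 9.7-10.3% for r = 0.3-0.7 (13 or 20 pairs, N = 264).

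**The case against.** Several points on the other side stand and limit the finding.

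- **The size is conditional.** The correlation and the number of pairs are assumptions. Only the direction follows from the documents. The plan also speaks of subjects and does not state the unit of this test outright.
- **The power loss does not carry over to radiographic success.** A reader might infer that a false ASES trigger costs radiographic power (90.2% at 112 per arm, 84.8% at 92). The plan separates bilateral subjects only for the outcome that triggered, so an ASES trigger leaves the radiographic analysis alone. The plan also allows additional enrolment to restore power.
- **Fisher's test is not clearly liberal.** It starts conservative. Simulated at N = 264 with 10 pairs, correlation 0.3-0.7 and the planned success rates, it runs from 7.3% to 10.2%. With 20-40 pairs it can reach about 15%. A patient-clustered robust test is no remedy: with 10 pairs and 7% failures it fired falsely in about 30-40% of trials, and with no bilateral failures its bilateral variance is zero.
- **The co-primary intervals are not the problem.** A reader might infer that "a 95% confidence interval for the difference between means in two independent samples" is invalid for the same reason. Because each shoulder is randomised separately, same-arm and opposite-arm pairs offset on average. For realised splits in the central 95% range the SE error stays within about 4%, with one-sided error about 4.4-5.6%.
- **Correlation is not the main source of false triggers.** The ASES interaction test keeps its level (about 9-10%), but either test can trigger. With 13 pairs at N = 264, the combined rule fires in about 19% of trials at zero correlation (1 − 0.9² = 19%) and 22-28% at 0.3-0.7. Correcting the t-test removes only the excess over about 19%.

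None of this makes the pooled t-test on shoulder-level ASES data a 10% test.

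**Conclusion.** The point holds for the ASES comparison of unilateral with bilateral subjects. Read with Randomization Details and Bilateral Patients, the named test treats a patient's two shoulders as independent although they always fall in the same group. Any positive correlation therefore puts the false-trigger rate above 10%. It is about 13-21% if the correlation is 0.3-0.7 and there are 5-40 pairs among 224 evaluable shoulders, and about 11-23% under wider assumptions. It is lower if patients with only one study shoulder count as bilateral.

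The consequence is an avoidable split of a co-primary analysis, or an avoidable amendment to enrol more subjects. The documents do not support reading this as a threat to the non-inferiority conclusion: ASES power remains near 98%, or 96% after a split with 20 pairs set aside, and no inflation of the non-inferiority type I error is shown.

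**What to change.** In the SAP, Tests for Interaction:

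1. Run the ASES unilateral-versus-bilateral comparison on one value per patient (the mean of the two study shoulders for a bilateral patient) with an unequal-variance t-test. Alternatively, use a mixed model with a patient effect.
2. State that bilateral here means that both of the patient's shoulders are in the study. The note after the Exclusion Criteria admits patients with an earlier contralateral replacement, so the term is otherwise open.
3. Keep Fisher's exact test for Radiographic Success and Absence of Revision/Removal/UADE. A robust or GEE test is unreliable with few pairs and few failures.
4. Leave the co-primary intervals under Efficacy Evaluations unchanged.

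The cost is SAP wording, minor programming and a slightly less sensitive ASES trigger. No extra data or patients are needed.
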